3.7 Control Group Intervention

The control group receives sham stimulation during the neuromodulation phase. All procedural steps are identical to those of the experimental group, including neuronavigation positioning, application of coupling gel, and all other preparatory procedures; however, ultrasound stimulation is not activated. Participants in the control group wear bone-conduction headphones to simulate and counteract acoustic confounding. Group allocation information is blinded to participants.

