3.5.5 Group Allocation

A total of 60 patients with hemiplegic upper limb dysfunction during the recovery phase of stroke, undergoing inpatient rehabilitation at the Department of Rehabilitation Medicine, Taizhou People's Hospital, will be randomly allocated into a neuromodulation group and a

control group (n = 30 per group) using a random number table. All participants in both groups will receive conventional pharmacological therapy (including antiplatelet aggregation agents, neurotrophic agents, circulatory improvement agents, plaque stabilizers, antihyperglycemic/antihypertensive agents, and supportive therapy) and standard rehabilitation interventions (physical therapy and occupational therapy). The neuromodulation group will receive one week of transcranial focused ultrasound stimulation in addition to conventional treatment. The control group will undergo the same assessment and procedural steps as the experimental group but will receive sham stimulation.

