Five neuromodulation sessions are administered in total. Sessions 2 and 5 involve simultaneous EEG-coupled ultrasound neuromodulation, while Sessions 1, 3, and 4 consist of ultrasound neuromodulation alone. During EEG-coupled sessions, EEG signals are acquired before, during, and after ultrasound stimulation; during standalone sessions, only ultrasound stimulation is delivered without EEG acquisition. Stimulation parameters are maintained at consistent control levels across participants. Based on each individual's

cranial acoustic parameters, the pre-attenuation stimulation intensity is back-calculated to ensure uniform in situ intensity at the target. The spatial-peak temporal-average intensity at the target is maintained below the diagnostic ultrasound safety threshold (720 mW/cm²). The ultrasound stimulation duration is 12 minutes using a 20% duty cycle pulse sequence.

The post-test cranial MRI protocol is identical to the pre-test and is performed within two days of completion of all neuromodulation sessions.

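### Section 3.7 specifies headphones for the control group only, while the protocol calls the procedures identical and does not say what the active arm wears

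*Protocol*

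**What the plan says.** Section 3.7 describes the sham. On procedure it says: "All procedural steps are identical to those of the experimental group, including neuronavigation positioning, application of coupling gel, and all other preparatory procedures". The stated exception is that "ultrasound stimulation is not activated". The next sentence adds an item of equipment: "Participants in the control group wear bone-conduction headphones to simulate and counteract acoustic confounding". The section closes with the protocol's only statement on blinding: "Group allocation information is blinded to participants".

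Section 3.5.5 makes the same claim of equal procedures: "The control group will undergo the same assessment and procedural steps as the experimental group but will receive sham stimulation". For the active arm it says only: "The neuromodulation group will receive one week of transcranial focused ultrasound stimulation in addition to conventional treatment".

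Section 3.6 describes the active sessions in detail (device, neuronavigation, room, stimulation timing, EEG) but mentions no headphones and no masking sound. On the recordings in Sessions 2 and 5 it says: "During EEG-coupled sessions, EEG signals are acquired before, during, and after ultrasound stimulation". Section 3.8 lists EEG spectral power and functional connectivity among the primary outcome measures, together with the upper-extremity Fugl-Meyer score.

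**The concern.** A sham works if the participant, and ideally everyone else at the session, cannot tell it from the active procedure. Equipment named for one arm only is an obvious way to tell them apart. Two things are at stake.

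- **Blinding.** No blinding of operators, outcome assessors or EEG analysts is stated, so the design relies on participants not knowing their arm. The Fugl-Meyer score depends partly on effort, and the comfort rating listed in the synopsis depends on expectation.
- **EEG.** If one arm receives sound through headphones and the other hears whatever the transducer emits, the arms differ in auditory input as well as in ultrasound while EEG is being recorded. An auditory response could then be read as neuromodulation.

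**Working it through.** No arithmetic decides this point, and the protocol gives no figure to reproduce. The check compares what is stated for each arm.

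| Feature | Active arm | Control arm |
|---|---|---|
| Ultrasound | On (3.5.5, 3.6) | Off (3.7) |
| Navigation, coupling gel, preparation | Done (3.6, 3.7) | Same (3.7) |
| Bone-conduction headphones | Not mentioned in the synopsis, 3.5.5, 3.6 or 3.7 | Worn (3.7) |
| Masking or simulated sound | Not mentioned | Through the headphones (3.7) |
| EEG before, during and after stimulation | Sessions 2 and 5 (3.6) | Same, by the equal-procedures sentences (3.5.5, 3.7) |

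**Step 1: consistency.** Section 3.7 says "All procedural steps are identical to those of the experimental group" and then names headphones for the control group. There are two possibilities. If the headphones are for controls only, the claim of identical procedures is wrong. If both arms wear them, the headphone sentence is wrong because it names one group. The text needs correcting either way.

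**Step 2: does the stated purpose fit?** The headphones are meant both to imitate and to counteract an acoustic confound. Imitation makes sense in the sham arm, where the transducer is silent. Counteracting does not, because there is no transducer sound to mask there. Masking could act only in the active arm, for which no headphones are specified. The soundproofed room in 3.6 limits outside noise; it does not remove sound from the transducer or the headphones.

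**Step 3: who could read the allocation?** Under the control-only reading, anyone present at a session can infer the arm from the headphones. A participant sees only their own sessions, and learns the arm only on finding out that headphones mark sham. A plausible route exists: participants are inpatients of one department (3.2, 3.5.5), and each has five sessions in the week.

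**Step 4: which EEG data are exposed?** Section 3.6 gives 480 trains of 0.5 s on and 1 s off, so 480 × (0.5 + 1) s = 720 s = 12 minutes, which matches the stated duration. If the transducer is audible, which is an assumption though the reference to an acoustic confound implies it, its sound would recur in step with stimulation throughout those 12 minutes. Under the control-only reading, the source and route of sound then coincide with arm during stimulation in Sessions 2 and 5, that is 2 of 5 sessions. A carry-over into recordings made just afterwards is possible. The pre-test EEG and the recording before stimulation in Session 2 are not directly affected. The study MRI is acquired outside the stimulation sessions, so headphone sound does not enter it directly. (An earlier paragraph of 3.6 has EEG recorded around each session. If that governs, all five sessions are exposed.)

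**The case against.** The strongest reply is that the protocol never says active participants go without headphones. Sections 3.5.5 and 3.7 both say the steps are the same, so the headphone sentence may be a loose description of equipment used in both arms. This stands in part. Control-only use is the natural reading of that sentence, but it is inferred from silence about the active arm. What can be supported is a contradiction or an unspecified point, not an established difference in what is worn.

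A reader might go on to infer that participant blinding fails and that allocation is visible for all 60 participants. The protocol does not support that. Headphones, or their absence, tell a participant nothing unless they know what they signify, and nothing shown says participants are told. The figure of 60 is the sample size, not an estimate of how many would be unblinded. Nor are headphones what would break operator blinding: no such blinding is claimed, and the protocol does not say that outcome assessors attend sessions.

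A reader might also infer that the EEG comparison is fully confounded. That too goes beyond the text. The headphones are intended to simulate the stimulation sound, so they may reduce the auditory difference; a silent sham could leave a larger one. What remains is a possible mismatch in the source, route and quality of sound, plus unmasked transducer sound in the active arm. Section 3.8 does not say that the recording during stimulation is the endpoint.

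These limits narrow the consequence but do not remove the contradiction in 3.7. The protocol gives no audio content, timing or volume that would show the arms to be matched.

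**Conclusion.** The point holds as a contradiction with two possible consequences. Section 3.7 gives headphones to controls only, 3.5.5 and 3.7 call the procedures the same, and 3.6 is silent for the active arm.

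If sites follow the text as written, equipment and sound delivery differ by arm. That puts participant blinding at risk and could add an auditory component to the EEG contrast during, and possibly just after, stimulation in Sessions 2 and 5. Neither effect can be sized from the protocol. The first depends on whether participants learn what the headphones mean, the second on how audible the transducer is and how closely the headphone sound imitates it. If both arms in fact wear the same headphones with the same audio, neither consequence follows and only the wording is at fault.

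It should be settled before enrolment, because a difference in sound between arms during recording cannot be separated from the effect of ultrasound afterwards.

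**What to change.** State in both 3.6 and 3.7 that participants in both groups wear the same bone-conduction headphones, with the same audio, timing and volume, at every session, so that ultrasound output is the only difference between arms. Reword the headphone sentence in 3.7 so that it no longer names the control group alone, and make the equal-procedures sentences in 3.5.5 and 3.7 agree with it.

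The cost is small: a sentence in each section, plus fitting the headphones and preparing the audio for active sessions. The sample size and the stimulation itself are unchanged. Section 6.1 requires ethics committee approval of the change. Section 8 schedules allocation from June 2026 and this version is dated April 27, 2026, so the stated timetable left room for it.

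Asking each participant after Session 5 which group they think they were in, and reporting the answers by arm, would be a useful check on blinding. It is optional, and its absence is not an error.

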Treatment Protocol	Neuromodulation Group: Multimodal neuromodulation targeting specific neural regions in addition to conventional therapy. Control Group: Sham stimulation in addition to conventional therapy.
Efficacy Assessment	Primary Outcome Measures: Fugl-Meyer Assessment score; neuroimaging data (cranial CT/MRI); EEG measurements of resting-state and task-state spectral power and functional connectivity; laboratory parameters (complete blood count, CRP, IL-6, S100 β , BDNF). Secondary Outcome Measures: Brunnstrom staging, Modified Ashworth Scale grading, muscle strength, and patient comfort assessment. Safety Assessment Indicators: Complete blood count, blood biochemistry, coagulation function.
Statistical Methods	Key outcome measures will be compared between the neuromodulation group and the control group before and after intervention using independent samples t-tests (two groups) or analysis of variance (multiple groups) to detect statistically significant intergroup differences. Non-parametric tests will be applied to data not conforming to a normal distribution.
Study Duration	March 2026 – March 2028

1. Background and Rationale

According to the World Health Organization (WHO), stroke is the second leading cause of death globally [1]. Approximately 15 million individuals worldwide experience a stroke annually, ranking second only to heart disease, and stroke remains one of the most prevalent causes of long-term disability. Ischemic stroke (IS) constitutes the most common subtype, accounting for approximately 85% of all stroke cases [2]. Among all stroke survivors, over 60% experience varying degrees of functional impairment within three months following the event. The American Stroke Association (ASA) has reported [3] that approximately one-third of stroke patients develop severe speech impairment post-stroke, while one in two patients sustains some degree of hand function loss. Stroke patients frequently contend with chronic functional deficits, including motor difficulties, speech impairment, and cognitive dysfunction, all of which profoundly compromise quality of life. These patients typically require prolonged rehabilitation and nursing care, imposing substantial financial burden on families and exerting considerable pressure on healthcare systems.

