3.1 Study Design

This study is a randomized, controlled, single-center trial.

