3.2 Sample Size

Participants will be recruited from inpatients of the Department of Rehabilitation Medicine. Based on preliminary literature review and the current inpatient volume of our department, the provisional sample size is set at $n = 60$, with 30 participants allocated to each group.

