3.8 Efficacy Assessment

Primary Outcome Measures: Post-treatment (immediate and 2-week follow-up) upper extremity Fugl-Meyer Assessment score, Brunnstrom staging, and Modified Ashworth Scale grading; neuroimaging data (analysis of ALFF, fALFF, ReHo, FC, and FA indices using functional MRI and diffusion tensor imaging); EEG measurements of resting-state and task-state spectral power and functional connectivity.

Secondary Outcome Measures: Blood biochemistry, complete blood count, C-reactive protein (CRP), interleukin-6 (IL-6), S100 β protein, and brain-derived neurotrophic factor (BDNF).

4. Risks and Benefits

4.1 Potential Risks and Mitigation Measures: Abnormal reactions to ultrasound stimulation and potential induction of seizures. Adverse symptoms such as dizziness and headache will be promptly managed. Short-term administration of analgesic agents and antiepileptic medications will be employed as indicated.

4.2 Potential Benefits and Compensation for Participants:

Direct Benefits: Promotion of hemiplegic upper limb functional recovery and enhancement of activities of daily living capacity.

Societal Benefits: It is anticipated that information obtained from this study may benefit the participant or future patients with similar conditions.

5. Adverse Event Monitoring

5.1 Adverse Events (AEs): An adverse event is defined as any unfavorable medical occurrence, unanticipated illness or injury, or unexpected clinical sign (including abnormal laboratory findings) in a participant or other individual, regardless of whether it is considered related to the study intervention or treatment strategy under investigation.

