November 2026 – August 2027: Continued case recruitment, statistical analysis of accumulated data, and objective evaluation of outcome measures across groups.

September 2027 – December 2027: Participation in provincial and national rehabilitation conferences, with preliminary findings presented for peer review and scholarly exchange.

January 2028 – February 2028: Continuation of clinical data collection, synthesis of completed research, comprehensive data analysis, and evaluation of study outcomes.

March 2028: Project completion, manuscript preparation, and publication.

9. Research Team

Name	Title / Specialty	Responsibilities
[name]	Chief Physician	Quality Control
[name]	Chief Physician	Data Analysis
[name]	Associate Chief Physician	Case Recruitment
[name]	Chief Physician	Data Analysis
[name]	Associate Chief Physician	Manuscript Preparation
[name]	Attending Physician	Case Recruitment
[name]	Attending Physician	Case Recruitment
[name]	Attending Physician	Case Recruitment
[name]	Attending Physician	Case Recruitment
[name]	Attending Physician	Rehabilitation Assessment
[name]	Senior Therapist	Rehabilitation Assessment

10. References

- [1] GBD 2021 Causes of Death Collaborators. Global burden of 288 causes of death and life expectancy decomposition in 204 countries and territories and 811 subnational locations, 1990–2021: a systematic analysis for the Global Burden of Disease Study 2021. *Lancet*. 2024;403(10440):2100.

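### Blinding is required for participants only; nothing requires that the raters of FMA-UE, Brunnstrom stage and MAS be unaware of the group

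*Protocol*

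**What the plan says.** Protocol section 3.7 (Control Group Intervention) holds the only statement on blinding: "Group allocation information is blinded to participants". Section 3.1 describes the design as follows: "This study is a randomized, controlled, single-center trial". Neither that section nor the synopsis calls the trial double-blind or assessor-blind.

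Section 3.7 defines the sham as the full set-up procedure with one difference: "however, ultrasound stimulation is not activated". It mentions bone-conduction headphones for the control group and says nothing of headphones for the active group.

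Section 3.8 opens its primary outcomes with "Post-treatment (immediate and 2-week follow-up) upper extremity Fugl-Meyer Assessment score, Brunnstrom staging, and Modified Ashworth Scale grading". The synopsis also makes the Fugl-Meyer score primary but places the other two scales lower: "Secondary Outcome Measures: Brunnstrom staging, Modified Ashworth Scale grading, muscle strength, and patient comfort assessment".

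Section 9 (Research Team) gives the duty "Rehabilitation Assessment" to two people, an attending physician and a senior therapist. Their rows are separate from those for recruitment and data analysis. No condition about knowledge of allocation is attached. On the setting, section 3.2 says: "Participants will be recruited from inpatients of the Department of Rehabilitation Medicine".

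**The concern.** FMA-UE, Brunnstrom stage and MAS are scored by a rater who watches or handles the limb and makes a judgement. A rater who knows the group and expects the stimulation to work can score borderline items more generously in one arm. That error has a direction. It adds to the treatment contrast, it does not shrink as patients are added, and it cannot be separated from a real effect once the scores are recorded.

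A sham controls what the patient expects. It protects a rater-scored endpoint fully only if the rater is also unaware of the arm. Here the allocation is easy to learn: the operator knows whether the device is on, and the headphones, as written, are a visible cue. The trial runs at one center among inpatients, and nothing keeps the assessors away from the sessions or the allocation list. The main clinical endpoint could thus be scored with the group known while the protocol is followed to the letter.

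**Working it through.** **Step 1: who is covered.** The protocol was read for any wording on blinding or masking of each role.

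| Role | Blinding stated? | Where |
|---|---|---|
| Participant | Yes | 3.7 |
| Raters of FMA-UE, Brunnstrom, MAS | No | 3.8 and 9 are silent |
| Person running the session | No; must know whether the device is on | 3.7 |

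**Step 2: which outcomes are exposed.** FMA-UE is a rater-scored primary outcome in both lists. Brunnstrom and MAS are primary in 3.8 and secondary in the synopsis, so only for Fugl-Meyer is primary status certain.

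**Step 3: how much a rating shift could matter.** The protocol gives no SD, alpha, effect size or expected bias, so it has no figure to reproduce. The inputs below are for illustration.

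- n = 30 per arm (sections 3.2 and 3.5.5).
- Two-sided alpha 0.05: assumed.
- SD of FMA-UE = 13: assumed. For orientation, a uniform spread over the eligibility range of 15 to 60 has SD 45/√12 = 13.0.
- No true effect. Knowing the group shifts post-treatment scores in one arm by b = 2 or 3 points on average: assumed.
- Correlation r between baseline and post-treatment score = 0.5 to 0.9: assumed, used only where baseline enters the analysis.

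False-positive rate = P(|Z + b/SE| > 1.96), with Z standard normal.

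Standard error of the group difference:

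- t-test on post-treatment scores: 13 × √(2/30) = 3.36
- ANCOVA: 3.36 × √(1 − r²), giving 2.91 (r = 0.5), 2.40 (r = 0.7), 1.46 (r = 0.9)
- t-test on change scores: 3.36 × √(2(1 − r)), giving 3.36, 2.60, 1.50

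| Analysis | b = 2 | b = 3 |
|---|---|---|
| Post-treatment t-test | 9% | 15% |
| ANCOVA, r = 0.5 | 11% | 18% |
| ANCOVA, r = 0.7 | 13% | 24% |
| ANCOVA, r = 0.9 | 28% | 54% |
| Change score, r = 0.5 | 9% | 15% |
| Change score, r = 0.7 | 12% | 21% |
| Change score, r = 0.9 | 27% | 52% |

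Example: for the post-treatment t-test with b = 2, b/SE = 2/3.36 = 0.60. The two tails are 0.086 + 0.005 = 0.092.

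The synopsis plans t-tests or analysis of variance, before and after the intervention. It does not name ANCOVA and does not settle whether change scores are meant. The post-treatment t-test is therefore the cautious reading, and the other rows show the range.

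**Step 4: the same without an assumed SD.** For the two-sample comparison the shift can be given in SD units, with SE = √(2/30) = 0.258. Shifts of 0.1, 0.2, 0.3 and 0.5 SD give false-positive rates of 6.7%, 12%, 21% and 49%. At SD 13, 2 points is 0.15 SD and 3 points is 0.23 SD.

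**The case against.** The strongest reply is that the protocol is silent about raters; it does not say that they know the allocation or attend sessions. That is right, and the point is confined to what the document fails to require. Silence is still a gap here, because who is blinded is a matter of design and conduct. A statistical analysis plan cannot blind a rater after the score is recorded.

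A second reply is that the sizes are assumed. That also stands. The documents give no SD, correlation or expected bias, and the highest percentages need r = 0.9 and an analysis that uses baseline. They are the top of a range.

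A third is that the sham still works on the patient's side, and that the EEG, MRI and blood measures are not judgement ratings. That is also true. The sham keeps part of its value, and the exposure is limited to the clinical scales.

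A reader might go further and infer from the section order (allocation in 3.5.5, pre-test in 3.6) that baseline scores too are rated after allocation. The document does not support this. Section 3.5.4 places the baseline scales at screening, section 3.4 uses them as entry criteria, and the order of the pre-test scales relative to allocation is not stated. Nor does section 9 say which department the two assessors belong to.

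**Conclusion.** The gap is real and should be closed before ratings begin. As written, the post-treatment FMA-UE, Brunnstrom and MAS scores may be given by staff who know the group, and a trial run exactly to protocol would have no defence against that for its main clinical endpoint.

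The conclusion rests on the text alone. The figures only show scale. With 30 per arm, SD 13 and a shift of 2 or 3 points, a nominal 5% error becomes about 9% or 15% on post-treatment scores. It can become several times the nominal level where baseline is used and r is high. Whether any bias will occur, and how large it would be, cannot be known from the document. It would be too strong to say that the raters are unblinded or that the sham is defeated.

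**What to change.** In sections 3.7 and 3.8, state that the two team members assigned to rehabilitation assessment in section 9:

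- are blinded to group allocation;
- have no access to the allocation list;
- neither attend nor deliver stimulation sessions.

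The cost is a few sentences and a separation of duties that section 9 already half makes, since assessment has its own rows. The downside is small: these two people cannot help at the sessions. Section 9 names no one to deliver stimulation, so some duties among the listed staff may have to be rearranged. Section 8 plans randomization from June 2026 and the protocol version is dated 27 April 2026, so on that timetable the wording can be in place before the first post-treatment rating.
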